### 10.3.7 Expected Outcomes

At the completion of this investigation we expect to find that improvements in functional mobility following community-based exercise will be driven by stage of motor dysfunction, peak lower-extremity joint angular displacement, and balance domain dysfunction at baseline (**Aim #1**) (Table 2). These findings will enable a revolutionary approach to rehabilitation for persons with PD, by targeting rehabilitation techniques focused on each individual's modifiable risk factor(s). Finally, we expect to find that by focusing our intervention on the domain of balance dysfunction that is most impaired in individual participants, we will reduce fall incidence (**Aim #2**). This will be a hallmark finding for the treatment of PD, as therapies thus far have been refractory to fall reduction.

**Table 2. Predictors of improvements in functional mobility**

Predictors	Modifying factor	Interpretation
Motor dysfunction	Higher UPDRS scores (more advanced PD)	We expect that mobility improvements will be greatest in individuals with more advanced UPDRS stages.  This may be due to decreased economy of movement in persons with more advanced PD. 
Balance domain dysfunction at baseline	Domain 3: Anticipatory postural control	Based on our preliminary data  we expect that individuals with anticipatory postural control deficits will see the greatest improvements in function
Knee and ankle joint angular displacement during gait	Peak joint angular displacement (range of motion)	Increases in peak knee and ankle angular displacement after exercise suggest that individuals with PD may move with greater flexibility and confidence 

## 10.4 Potential Problems & Alternative Approaches

One potential problem with this clinical trial is that dropouts may occur. Our prior experience with longitudinal exercise studies suggests that we can expect a dropout rate between 5-20%. We have anticipated a very conservative 20% rate, and will recruit 4 additional participants over our sample size of 20. This will ensure an appropriate number of subjects completing the study to maintain the desired statistical power.

While we are attempting to limit the variability in participant outcomes by constraining inclusion criteria to persons with mild to moderate PD, this also poses a challenge in that many participants who volunteer for exercise studies are likely to be physically active individuals, which has the potential to dilute our treatment effect. This recruitment bias may also mean that few of these individuals will have experienced falls at baseline. In the event that non-statistically significant results appear, we have planned our analysis such that we can utilize clinically significant outcomes (eg., effect sizes) to overcome any potential recruitment bias and demonstrate the clinical impact of the intervention.

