#### 10.3.6 Sample size and Statistical analysis

Aim# 1 is the primary aim and based on our preliminary data with alpha=.05, a sample size of 20 will give 84% power to detect a relationship with an effect size of  $r=.60$ . The prevalence of PD in industrialized countries is estimated to be about 0.3%. Using this estimation, we anticipate there to be approximately 2,129 persons in the Boise area with PD. Based on these factors we anticipate fully meeting our recruitment needs.

For Aim #1, the goal is to explore the relationship between modifiable factors and outcomes. Initially because of the exploratory nature of these explorations, change scores for the outcome measures will be

constructed. Bi-variate correlations, parametric and non-parametric as appropriate, will be used to assess the strength of the relationship between individual outcome change scores and the modifiable factors. These results may be confounded by the progression of the disease, especially at the later measurement. Change in disease state will be introduced as a possible influence in partial correlations between modifiable factors and outcomes. Effect sizes will be calculate using Cohen's  $d$ .

For Aim #2 the interest is in the reduction of falls among this patient population. Initially to examine the changes in the number of falls a non-parametric McNemar test of change will be used. To examine other factors outside of the intervention that could influence the outcome will follow-up the analyses with McNemar test stratified by possible confounders (i.e. progression of the disease, continuation of the exercise regimen).

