10.3 Approach

10.3.6 Sample size and Statistical analysis

Aim# 1 is the primary aim and based on our preliminary data with alpha=.05, a sample size of 20 will give 84% power to detect a relationship with an effect size of $r=.60$. The prevalence of PD in industrialized countries is estimated to be about 0.3%.¹ Using this estimation, we anticipate there to be approximately 2,129 persons in the Boise area with PD. Based on these factors we anticipate fully meeting our recruitment needs.

For Aim #1, the goal is to explore the relationship between modifiable factors and outcomes. Initially because of the exploratory nature of these explorations, change scores for the outcome measures will be constructed. Bi-variate correlations, parametric and non-parametric as appropriate, will be used to assess the strength of the relationship between individual outcome change scores and the modifiable factors. These results may be confounded by the progression of the disease, especially at the later measurement. Change in disease state will be introduced as a possible influence in partial correlations between modifiable factors and outcomes. Effect sizes will be calculate using Cohen's d .

For Aim #2 the interest is in the reduction of falls among this patient population. Initially to examine the changes in the number of falls a non-parametric McNemar test of change will be used. To examine other factors outside of the intervention that could influence the outcome will follow-up the analyses with McNemar test stratified by possible confounders (i.e. progression of the disease, continuation of the exercise regimen).

Reference

1. de Lau LM, Breteler MM. Epidemiology of Parkinson's disease. *The Lancet Neurology*. Jun 2006;5(6):525-35. doi:10.1016/s1474-4422(06)70471-9

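### Four extra recruits do not cover the plan's own 20% dropout rate: 24 × 0.80 = 19.2 expected completers, so power at r = .60 is about 81% rather than 84% (minor)

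*Protocol*

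**What the plan says.** Section 10.3.6, in the same words in the protocol and the SAP, sets the target for the primary aim: "a sample size of 20 will give 84% power to detect a relationship with an effect size of" r = .60, at alpha .05. The analysis for that aim correlates change scores in the outcomes with modifiable factors.

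Protocol section 10.4 deals with attrition. It gives a range, "Our prior experience with longitudinal exercise studies suggests that we can expect a dropout rate between 5-20" per cent, and then picks the upper end: "We have anticipated a very conservative 20% rate, and will recruit 4 additional participants over our sample size of 20". It concludes: "This will ensure an appropriate number of subjects completing the study to maintain the desired statistical power".

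The 20 is therefore a number of completers, the recruitment total is 24, and the planning rate is 20%. Neither document gives another recruitment total or another dropout allowance.

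**The concern.** The planning rate, the allowance and the assurance do not agree. Adding 4 to 20 is the calculation 20 × 1.20, which takes the dropout percentage of the final number. Dropout applies to those enrolled, so the target should be divided by the retention fraction. At the rate the protocol says it planned for, the expected number of completers falls below the number on which the 84% rests.

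What is at stake is small: whether section 10.4 describes the power correctly at its own planning rate. Neither the choice of analysis nor the feasibility of the study is in question.

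**Working it through.** **Inputs.** Target n = 20, power 84%, r = .60 and alpha = .05 come from section 10.3.6 (protocol and SAP). Dropout of 5–20%, the planning rate of 20% and the 4 extra recruits come from protocol section 10.4. Two assumptions are added: the test is two-sided (sidedness is not stated), and a participant who drops out contributes no change score.

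**1. Reproduce the stated power.** The null hypothesis ρ = 0 is rejected when |r| exceeds t/√(n − 2 + t²), where t is the two-sided 5% critical value on n − 2 degrees of freedom. Power is the probability of rejection under the exact bivariate-normal distribution of the sample correlation with ρ = .60.

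- n = 20: 83.6%, which rounds to the stated 84%.
- One-sided exact at n = 20: 90.4%, which does not match. This is why two-sided is assumed.
- Fisher z approximation, two-sided, at n = 20: 81.5%, which does not match either.

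The stated figure is right for 20 completers.

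**2. Check the inflation step.**

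- As planned: 20 × 1.20 = 24 recruits.
- Expected completers at 20% dropout: 24 × 0.80 = 19.2, which is 0.8 short of 20.
- Recruits needed for 20 expected completers: 20/0.80 = 25.
- Largest loss that leaves 20 of 24: 4/24 = 16.7%. A fifth loss is 5/24 = 20.8%.

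**3. Power at the planning rate**, by the method that reproduces 84%.

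- n = 19: 81.4%.
- n = 19.2 (formula evaluated at the non-integer value): 81.9%.
- Averaged over a Binomial(24, 0.80) number of completers: 81.4%.

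About 81% thus refers to 19 whole completers or to the average over random dropout.

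**4. Across the protocol's range.** Each participant is taken to drop out independently with the stated probability.

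| Recruits | Dropout | Expected completers | Chance of at least 20 | Average power |
|---|---|---|---|---|
| 24 | 5% | 22.8 | 99.4% | 88.3% |
| 24 | 10% | 21.6 | 91.5% | 86.3% |
| 24 | 12.5% | 21.0 | 82.7% | 85.2% |
| 24 | 20% | 19.2 | 46.0% | 81.4% |
| 25 | 20% | 20.0 | 61.7% | 83.1% |

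At the planning rate, 24 recruits are slightly more likely than not to leave fewer than 20 completers.

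**The case against.** The best case for leaving the text alone is that the slip has almost no consequence.

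- **The rate is a worst case.** The protocol calls 20% very conservative, and section 10.3.1 reports no dropout in the team's earlier 18-week programme. With 24 recruits, average power exceeds 84% at 5%, 10% and 12.5% dropout. This stands, and it is why the point is minor. It does not rescue the assurance, because section 10.4 names 20% as the rate it allowed for.
- **The loss is within the uncertainty of the method.** Changing from the exact test to Fisher z at n = 20 moves power by 83.6 − 81.5 = 2.1 points, about as much as losing one completer (83.6 − 81.4 = 2.2). The primary analysis is also exploratory and may use non-parametric or partial correlations. This too is fair, and the 84% is nominal. The shortfall of 19.2 against 20 does not depend on the test.
- **Some dropouts may still give data.** Someone who leaves after the 6-week assessment could supply a change score from baseline to week 6. That softens the loss for that interval, but the change score to the end of training would still be missing.
- **Twenty-five recruits would not ensure 20 completers either.** Correct: the chance is 62% at 20% dropout. This favours correcting the wording over relying on the extra recruit.

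**Conclusion.** The concern holds, and it is minor. At 20% dropout the plan is one recruit short: 24 give 19.2 expected completers, and power at r = .60 is about 81% instead of 84%. Neither document sets a minimum power that is missed, and power stays above 80% by the method that reproduces the plan's figure. Expected completers reach 20 for any dropout up to 16.7%, which is most of the 5–20% range.

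The power figures rest on a two-sided exact test of a single bivariate correlation and on dropouts contributing no change score. The probabilities also assume independent dropout. The completer count needs only the plan's own rate, applied to those enrolled.

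**What to change.** Keep 24 and replace the sentence "This will ensure an appropriate number of subjects completing the study to maintain the desired statistical power" in protocol section 10.4 with something like:

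> At 20% dropout, 24 recruits give 19.2 expected completers. With 19 completers, power for the bivariate correlation at r = .60 is about 81% (two-sided alpha .05). Twenty completers, and 84% power, are kept if no more than 4 of the 24 (16.7%) drop out.

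This costs only wording.

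The alternative is to recruit 25 (20/0.80), at the cost of one more participant. Expected completers are then 20 at 20% dropout, but the text should still not promise that number, since the chance of reaching it is 62%. Section 10.3.6 can stay as it is under either option, because its 84% is stated for 20 participants and is correct for that number.

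### Aim #1: a correlation on change to T12 cannot include participants without a T12 visit or use their T6 data, and four extra recruits are the only stated answer to dropout

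*Protocol*

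**What the plan says.** Section 10.3.6 reads the same in the Protocol and the SAP. It names Aim #1 as primary and states that "a sample size of 20 will give 84% power to detect a relationship with an effect size of" r=.60. On the analysis, "change scores for the outcome measures will be constructed", and these are related to the modifiable factors by bivariate correlations, parametric or non-parametric, and then by partial correlations that allow for change in disease state. The section gives no interval for the change score and no analysis set. It does mention a later measurement when warning about disease progression, so change may be examined at more than one visit.

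Protocol 10.3.4 schedules assessments at T0, T6 and T12. Protocol 10.4 deals with dropout: "we can expect a dropout rate between 5-20" per cent, planned at 20%. The answer is that the team "will recruit 4 additional participants over our sample size of 20. This will ensure an appropriate number of subjects completing the study", with the stated purpose of keeping the intended power. Neither document gives a missing-data method, a use for partial follow-up or a dropout sensitivity analysis. Table 2 (Protocol 10.3.7) predicts the largest mobility gains in participants with higher UPDRS scores.

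**The concern.** Over-recruitment replaces numbers. It does not deal with who is lost. A change score to T12 does not exist for someone without T12, so that person drops out of the correlation even if T0 and T6 were measured. Correlating T6 change separately would use those values for a T6 question, but would lend nothing to the T12 result.

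Two things are at stake. Some information already collected goes unused. And if leaving depends on both severity and response, the people left at T12 can show a severity-response relationship that differs from the one in everybody enrolled. Protocol 10.5 intends the results to support an application for a randomised trial, so an artefact of this kind would be carried forward.

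**Working it through.** **Inputs from the documents.** n=20, r=.60, alpha .05, power 84% (10.3.6); dropout 5-20%, planned at 20%, four extra recruits (10.4); visits T0, T6, T12 (10.3.4). The dropout mechanisms and the T6-T12 correlation of change are not in the documents and are assumed below.

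**1. The stated power.** For a two-sided test of a Pearson correlation at r=.60, the exact bivariate-normal calculation gives 83.6% at n=20. The 84% is reproduced. At n=19 the same calculation gives 81.4%.

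**2. The head-count.**
- Enrolled: 20 + 4 = 24.
- Expected completers at 20% dropout: 24 x 0.80 = 19.2; at 5%: 24 x 0.95 = 22.8.
- Chance of at least 20 completers, independent dropout: 46% at 20%, 99% at 5%.
- Enrolment for 20 expected completers at 20% dropout: 20 / 0.80 = 25.

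**3. Information in T6.** Let f be the fraction without T12, all of them seen at T6, and ρ the correlation of T6 and T12 change given the factor. With random dropout, the variance of the likelihood slope relative to the completer slope is about (1 - ρ²) + ρ²(1 - f) = 1 - fρ².
- f=.20, ρ=.6: 1 - .20 x .36 = .928, efficiency 1/.928 = 1.08.
- f=.20, ρ=.8: 1 - .20 x .64 = .872, efficiency 1/.872 = 1.15.

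Simulation with 5 of 24 lost agrees: standard errors .247 against .237 (ρ=.6) and .248 against .231 (ρ=.8), that is (.247/.237)² = 1.09 and (.248/.231)² = 1.15. Across simulations the ratio ran from 1.05 to 1.20. The bottom of that range is also what results at ρ=.6 if only half the leavers are seen at T6.

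**4. Bias with no true relationship.** Simulation: 24 enrolled; logistic dropout on standardised severity and T6 response with coefficients of 1, calibrated to 20%; ρ=.6 / .8.

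| Who leaves | Mean completer r |
|---|---|
| High UPDRS and poor T6 response | about +.05 / +.07 (up to +.09 in a parallel run) |
| Low UPDRS and poor T6 response | about -.06 / -.07 |
| Depends on severity alone, or response alone | about 0 |
| First row, 5% dropout | about +.02 |

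In the first row, false positives in the predicted direction are 3.8% / 4.6% against 2.5%. Those in the opposite direction fall to about 1%, so the total two-sided error is about 5-6% against 5%. The likelihood slope that uses T6 has bias within .01.

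**5. Stronger and different mechanisms** (5 of 24 lost by rank, some random noise).
- Severity plus poor T6 response: completer slope +.09 / +.13 / +.18 at ρ = .4 / .6 / .8; about 0 when T6 is used.
- Severity plus poor T12 response, which is not observed: completer r .22, predicted-direction false positives about 16%. The slope bias of about .22 falls only to .19 / .15 / .09 when T6 is used.
- True r=.60, dropout on severity alone or response alone: completer r about .51, against .59 with random dropout.

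**The case against.** A reader might infer that the plan analyses T12 minus T0 in completers and discards leavers' T6 data. The documents do not say so. The interval and analysis set are simply unstated, the mention of a later measurement suggests that T6 change may have its own correlation, and the phrase about completing the study in 10.4 justifies recruitment rather than defining an analysis set. What can be said is narrower: a correlation on change to T12 cannot contain these people, whatever else is done with T6.

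A reader might also infer that dropout pushes the result toward the Table 2 prediction. That needs high-UPDRS poor responders to be the ones who leave. Nothing in the documents supports that pattern over its reverse, and Protocol 10.3.1 reports no dropout in an earlier 18-week programme. Under the moderate mechanism the shift is small beside a standard error of about .25, and 10.4 itself regards 20% as conservative.

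It is also fair to say that Aim #1 is exploratory, that the efficiency gain is modest and confined to leavers seen at T6, and that a mixed model at about 20 people brings assumptions of its own. Nor does it suit the range-of-motion row of Table 2 if the factor there is a change after exercise, since a leaver then lacks the factor too. These points limit the size of the concern and the scope of the remedy. They do not supply the missing rule for incomplete follow-up.

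**Conclusion.** The point holds as a gap in the analysis plan with an inexpensive improvement available. It is not a demonstrated bias in favour of the hypothesis. The exclusion of people without T12 from a T12 change correlation follows from the method itself. Its size and direction rest on assumed mechanisms: a modest loss of efficiency, and a bias that may be upward, downward or absent, small under moderate selection and larger only under strong joint selection.

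Separately, at the plan's own 20% rate the head-count is more likely than not to fall below 20. The cost is about two points of power (83.6% to 81.4% at 19), but the wording promises more than 24 recruits deliver.

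**What to change.** - State the change interval, the analysis set and the handling of incomplete follow-up for Aim #1.
- For continuous outcomes with a baseline factor (UPDRS, balance domain, baseline gait and range of motion), make the T12 test the factor-by-visit term at T12 in a linear mixed model on T0, T6 and T12. Use unstructured covariance and Kenward-Roger degrees of freedom, and include everyone with T0 data. With no dropout this gives the same slope as regressing the change score on the factor.
- Invite participants who stop training to the T6 and T12 assessments already scheduled. This is the main protection where dropout depends on the T12 response.
- Report the planned parametric or non-parametric correlations in completers as a sensitivity analysis.
- Where the factor is itself a post-exercise change (Table 2, range of motion), keep the correlation and label it completer-only.
- In 10.4, soften the assurance on power, or restate power as about 81% at 19 completers.

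Cost: SAP wording, slightly more analysis, and reliance on normality at about 20 people. No new visits. The model does not fully remove bias if dropout depends on the unseen T12 response, and the write-up should say so.

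### Protocol 10.4 says effect sizes can overcome recruitment bias and demonstrate clinical impact when results are non-significant; effect sizes from the same volunteers can do neither

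*Protocol*

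**What the plan says.** Protocol 10.4 notes that people who volunteer for exercise studies tend to be active, which could dilute the treatment effect. It adds: "This recruitment bias may also mean that few of these individuals will have experienced falls at baseline". It then turns to what happens if results are not statistically significant, and says the analysis has been planned so that it can "utilize clinically significant outcomes (eg., effect sizes) to overcome any potential recruitment bias and demonstrate the clinical impact of the intervention".

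Section 10.3.6, which has the same text in the Protocol and the SAP, is where that analysis would be found. For Aim #1 it plans correlations between change scores and modifiable factors, with partial correlations for change in disease state. It states that "a sample size of 20 will give 84% power to detect a relationship" of r=.60, and later that "Effect sizes will be calculate using Cohen's" d. For Aim #2: "Initially to examine the changes in the number of falls a non-parametric McNemar test of change will be used". It gives no confidence interval for any effect size, no SD for Cohen's d, no effect size for McNemar's test and no adjustment for who volunteers. It states neither the version nor the sidedness of McNemar's test.

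Protocol 10.3.3 describes one group receiving the programme. Protocol 10.5 leaves a randomised comparison to a later application.

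**The concern.** The sentence in 10.4 is a rule of interpretation fixed in advance, and it makes two claims. One is that an effect size removes or offsets a recruitment bias. The other is that an effect size can establish clinical impact when the test has not shown an effect. If the rule is followed, a result compatible with no change is reported as demonstrated impact, and so is a result from too few fallers to be informative. Protocol 10.5 says that accomplishing the aims will support an application for a randomised trial, so an overstated result here would feed into that case.

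**Working it through.** **Inputs.** n=20, alpha=.05, r=.60 and 84% power come from 10.3.6. Sidedness is not stated. The possible shortage of baseline fallers comes from Protocol 10.4. No baseline fall rate is given.

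**The plan's own figure.** Section 10.4 attaches no number to the fallback. The 84% in 10.3.6 reproduces for one two-sided Pearson correlation (83.6% by bivariate-normal simulation), so two-sided .05 is used for the correlations below.

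**1. Can an effect size overcome the selection?** For a correlation, t = r√(n−2)/√(1−r²), so the p-value is fixed by r and n. For McNemar's test, the p-value is fixed by the numbers changing in each direction. In both cases the effect size and the test are computed from the same observations in the same people. If active volunteers improve less, the effect size describes that smaller improvement. Removing the bias would need different recruitment, weighting or outside information, and 10.3.6 contains none of these.

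**2. Can a non-significant correlation demonstrate impact?**
- Critical value: t(18)=2.101, so r = 2.101/√(18+2.101²) = 0.444. Any |r| below this is non-significant.
- Example r=0.40: t = 0.40×√18/√(1−0.16) = 1.85, p=.081.
- Fisher interval: atanh(0.40) ± 1.96/√17 = 0.424 ± 0.475. Back-transformed, this is −0.05 to 0.72.

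The interval runs from slightly below zero to above the planned .60. It cannot support a claim of demonstrated effect, nor does it show absence of one.

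**3. Falls.** Assume McNemar's test is applied to faller yes/no. If 5 people stop falling and none start:

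| Version | Calculation | p |
|---|---|---|
| Two-sided exact | 2×0.5⁵ | .0625 |
| Continuity-corrected | χ² = (5−1)²/5 = 3.2 | .074 |
| One-sided exact | 0.5⁵ | .031 |
| Uncorrected | χ² = 5²/5 = 5 | .025 |

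The number who stop cannot exceed the number of baseline fallers. With 5 or fewer, a significant reduction is therefore out of reach under the first two versions. Under the one-sided exact test the limit is 4 or fewer (0.5⁴=.0625). Under the uncorrected test it is 3 or fewer (χ²=3, p=.083).

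For 5 versus 0, the exact two-sided 95% interval for the ratio of improvers to worseners starts at 0.92: the lower proportion is .025^(1/5)=.478, and .478/.522=0.92. Even this one-directional pattern includes a ratio of 1.

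How often there would be 5 or fewer fallers depends on an assumed rate. If 10%, 20% or 30% of 20 participants fell at baseline, the binomial probability is 99%, 80% or 42%.

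**The case against.** Reporting effect sizes is good practice, particularly in a small study, and 10.3.6 already plans Cohen's d without making it conditional on a p-value. The abbreviation for *for example* in 10.4 leaves room for other clinical outcomes. The sentence sits in a contingency paragraph of the Protocol, and the SAP section does not repeat it. A Cohen's d of mean change could also exclude zero when a correlation does not.

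Much of this stands. Effect sizes should stay, and a reader who inferred that they are calculated only after a failed test would be going beyond the text. But no other clinical outcome is named as the fallback and no threshold of clinical importance is set, and any outcome from these volunteers shares their selection. A d of mean change answers a different question from Aim #1, which concerns relationships, and without a comparison group it cannot separate the programme from other causes of change.

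Three further inferences are tempting and not supported:
- That the Protocol expects few fallers. It says only that this may happen.
- That McNemar's test could not succeed. This depends on a version and sidedness that are not stated. The stated interest is in reduction, so a one-sided test cannot be excluded.
- That the loss from dilution can be put in figures. The documents give nothing to size it, and an equal reduction in everyone's change would leave a correlation unaltered.

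**Conclusion.** The point holds. Both claims in the last sentence of 10.4, that effect sizes overcome recruitment bias and that they demonstrate impact after a non-significant result, are wrong as written. The first fails whatever the numbers, because the estimate comes from the same self-selected, single-group participants. The second fails because a non-significant estimate has a matching 95% interval that includes no effect. At n=20 this covers every |r| below 0.444, taking a two-sided .05 test of a Pearson correlation.

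For falls the conclusion is more limited. With few baseline fallers a non-significant result is plausible, and an effect size cannot supply the missing information. The McNemar figures assume faller yes/no coding and differ by version.

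A reader might infer that the plan names no effect size suited to Aim #1. It does name r, in the power statement, as well as Cohen's d. The gaps are the missing intervals, the unstated SD for d and the absence of an effect size for McNemar's test. The matter is one of interpretation and reporting; it does not call the sample size or the choice of outcomes into question.

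**What to change.** Replace the last sentence of Protocol 10.4 with:

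> Effect sizes with 95% CIs will be reported for every outcome whatever the p-value; a non-significant result will be interpreted from its CI and will not be described as demonstrating clinical impact; because the study is single-group, pre-post change will not by itself be attributed to the intervention; recruitment of active volunteers will be reported as a limitation on generalisability and on sensitivity to change.

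In 10.3.6 of both documents:
- report r with its confidence interval for the correlations;
- state the SD used for Cohen's d;
- for McNemar's test, state the version and sidedness, and report the numbers changing in each direction with an interval.

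The cost is wording only, with no added data or participants. The downside for the sponsor is that a non-significant result can no longer be presented as demonstrated impact.
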